## **4. SELECTION AND WITHDRAWAL OF PARTICIPANTS**

### **4.1 PRE-RANDOMISATION OR PRE-REGISTRATION EVALUATIONS**

Mass treatment of the whole community with azithromycin is recommended for the purpose of yaws control. Mass treatment of the whole community with Ivermectin and Permethrin is the best available treatment for the purpose of scabies control. Both treatment are offered to all individuals regardless of the presence/absence of clinical features of either disease – which is in line with the best evidence on how community mass treatment for these diseases should be conducted.

### **4.2 INCLUSION CRITERIA**

All consenting individuals in the participating communities will eligible to participate

### **4.3 EXCLUSION CRITERIA.**

Individuals not consenting to participate in the study.

Individuals who are unwell on the day that study medications are administered.

### **4.4 WITHDRAWAL CRITERIA**

Study participation is voluntary and study participants can withdraw at any time. The number of withdrawals will be recorded and only data collected prior to withdrawal will be included in the analysis. Only data collected prior to withdrawal will be included in the analysis. 

## **5. RANDOMISATION AND ENROLMENT PROCEDURE**

### **5.1 RANDOMISATION OR REGISTRATION PRACTICALITIES**

Randomisation will be done at the level of the community by drawing sealed envelopes. All individuals within a community will be offered treatment in line with the randomisation of that community. All residents of the selected communities will be invited to participate in the study.

#### Community Awareness

Prior to the study commencing we will engage community leaders and local health staff from communities in the catchment area of AAH. A research training workshop will be held at AAH and which will be attended by AAH and other study staff as well as key community leaders. This meeting will provide an opportunity for explanation of the study aims and methodologies and for study staff to answer questions about the study design and implementation.

#### Eligibility Criteria:

All individuals within a community will be offered treatment in line with the randomisation of that community. All residents of the selected communities will be invited to participate in the study.

#### Inclusion Criteria:

All residents of the selected communities will be invited to participate in the study.

#### Exclusion Criteria:

Individuals with a contra-indication to treatment.  
Individuals not consenting to participate.

### **5.2 BLINDING**

This is an open-label study

## 6. TRIAL MEDICATION

### 6.1 Name and description of investigational medicinal product(s)

#### Azithromycin

Azithromycin is an azalide antibiotic, a subclass of the macrolides. After oral administration, peak plasma concentration is reached in 2 to 3 hours. Tissue levels of azithromycin are greater than plasma levels (up to 50 times the maximum plasma concentration). Biotransformation occurs mainly in the liver, with elimination mainly by the bile and partly by urine. The plasma terminal half-life is 2-4 days. Azithromycin is indicated for mild to moderate infections such as respiratory-tract infections, otitis media, skin and soft-tissue infections and genital chlamydial infections. Azithromycin is the treatment of choice for mass treatment of both yaws and trachoma. The recommended dose for the mass treatment of yaws is a single-dose of azithromycin 30mg/kg up to a maximum of 2g. Azithromycin is available as 250 mg or 500 mg tablets and as oral suspension.

#### Ivermectin

Ivermectin is an anthelmintic. Ivermectin is metabolized in the liver, and ivermectin and/or its metabolites are excreted almost exclusively in the feces over an estimated 12 days, with less than 1% of the administered dose excreted in the urine. After oral administration, the apparent plasma half-life of ivermectin is approximately 16 hours. Ivermectin is indicated for the treatment of onchocerciasis or river blindness caused by *Onchocerca volvulus* and for strongyloidiasis caused by *Strongyloides stercoralis*. The recommended dosage for treatment of scabies is two oral doses designed to provide approximately 200µg of ivermectin per kg of body weight. The same dose is recommended in the Solomon Islands. Ivermectin is available in 3mg tablets.

#### Topical 5% permethrin cream (Lyclear®)

Topical 5% permethrin (Lyclear®) cream for scabies is supplied in a 30g tube. The cream is applied all over the body including from neck to toe and washed off after a minimum of 8 hrs. For children aged 2 months or less permethrin should be washed off after 4 hours.

### 6.2 Legal status of drug

Azithromycin is licensed for use in the UK. It is listed on the essential medicines list of the Solomon Islands and is the WHO recommended drug for community mass treatment for yaws eradication.

Permethrin is licenced in the UK for the treatment of scabies. It is listed as on the essential medicines list for the Solomon Islands and recommended as a potential treatment for scabies.

Ivermectin is not licenced for the treatment of scabies in the UK although NICE has provided guidance on its use (<https://www.nice.org.uk/advice/esuom29/resources/ivermectin-for-difficulttotreat-scabies-17546902981>). Ivermectin is widely used in control programmes for both Onchocerciasis and Lymphatic Filariasis. Ivermectin is listed as on the essential medicines list for the Solomon Islands and recommended as a potential treatment for scabies.

**6.3** Summary of Product Characteristics (SmPC) or Investigator Brochure (IB)  
Product Characteristics Sheets are attached in the Appendix.

**6.4** Drug Storage and Supply  
Medications will arrive by plane and will reach the islands by boat at the provincial pharmacy / medical store. The order request will be checked with the supplies delivered. The delivery notice number, delivery date and the medications batch number will be recorded in a log book. Medications will be taken out of the pharmacy in bulk by the study teams for dispensing in the community. Study teams will maintain a log of all medicines dispensed that can be cross-checked against participants study records.

**6.5** Preparation and labelling of IMP  
For participants receiving ivermectin and azithromycin, the dose will be determined according to body weight and treatment will be administered under direct supervision of the study team. Drug administration will be recorded in a standardized record form.

Participants assigned to permethrin (due to contra-indication to ivermectin) will receive a tube of cream and will be asked apply the cream from neck to toes before they leave the clinic and under supervision of a study nurse, and leave it on for a minimum of 8 hours, maximum 24 hours if possible. For children aged 2 months or less, cream will applied for a maximum of 4 hours.

**6.6** Dosage schedules/modifications  
In line with standard treatment the dosing of both Azithromycin and Ivermectin will use the following weight bands

WEIGHT	AZITHROMYCIN TABLETS (250mg Tabs)	IVERMECTIN TABLETS (3mg Tabs)
<15KG	1	PERMETHRIN CREAM
12.5-15 – 25 KG	1	1
25 – 37.5 KG	2	2
37.5 – 50 KG	3	3
50-75 KG	4	4
>75 KG	4	5

Formatted: Font: Bold

Permethrin will be used instead of Ivermectin in the following circumstances

- Pregnancy
- Breastfeeding
- Child <6 months age
- Child <12.5kg

Formatted: Font: Bold

Where permethrin is indicated the following standard dosing protocol will be used:

- Full tube for adults.
- Half tube for children.
- Apply to whole body and leave on for 1 day before washing off

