### *Treatment of scabies:*

Either an oral dose of Ivermectin (200µg/kg) or permethrin cream for those with a contraindication to Ivermectin (WT<15kg, pregnant or breastfeeding women) given in 2 doses 7-14 days apart.

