## 6.8 Concomitant medication

Individuals receiving Warfarin may not receive treatment with Ivermectin due to potential interactions.

No individuals outside of the capital of the Solomon Islands (Honiara) are receiving Warfarin due to a lack of INR monitoring facilities and therefore it is not anticipated that any individuals in the study will be receiving a contra-indicated concomitant medication.

**6.9** Trial restrictions

There are no trial restrictions.

As noted above pregnant and breast feeding women and children <15kg will be offered permethrin rather than ivermectin but will still be allowed to participate in the study.

**6.10** Assessment of compliance

Drugs will be delivered as a single observed treatment and therefore compliance will be assessed at the time of drug distribution.

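### Above 15 kg, the Section 6.6 ivermectin row ending at 25 kg gives less than the stated 200 µg/kg, and the weights 25, 37.5 and 50 kg each map to two tablet counts

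*Combined protocol and SAP*

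**What the plan says.** The per-kilogram dose appears in three places. The Study Summary and the scabies treatment paragraph of Section 3 give it without qualification: "Either an oral dose of Ivermectin (200µg/kg) or permethrin cream", "given in 2 doses 7-14 days apart". The ivermectin paragraph of Section 6.1 softens it slightly, describing "two oral doses designed to provide approximately 200µg of ivermectin per kg of body weight", and adds that "Ivermectin is available in 3mg tablets".

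Section 6.6 turns this into tablets, stating that "the dosing of both Azithromycin and Ivermectin will use the following weight bands". The ivermectin column reads:

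- under 15 kg: "PERMETHRIN CREAM"
- row printed as 12.5-15 – 25 KG: 1 tablet
- 25 to 37.5 kg: 2 tablets
- 37.5 to 50 kg: 3 tablets
- 50 to 75 kg: 4 tablets
- above 75 kg: 5 tablets

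The list under the table switches to permethrin at "Child <12.5kg". Section 6.9 says instead that "pregnant and breast feeding women and children <15kg will be offered permethrin rather than ivermectin", which agrees with the limit in the Study Summary and Section 3.

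No section gives a tolerance around 200 µg/kg, and none says which row applies to a weight that stands at the end of two rows.

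**The concern.** The table is the operative rule. Sections 6.5 and 8 have each person weighed and then treated under observation according to the schedule. If the table and the per-kilogram statements disagree, teams will deliver what the table says, while the rest of the protocol, and any report that repeats it, will describe something else.

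The disagreement is worth checking because scabies treatment is the common background of both arms and the only mass treatment that the sequential arm receives on Day 1. Section 1.1 links scabies to secondary impetigo, which is the primary outcome. The row in question mainly concerns children, and a two-dose course applies the same row twice.

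The second issue is practical: where two rows share an end point, two teams can follow the same chart correctly and hand out different numbers of tablets.

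**Working it through.** **Inputs.** Tablet strength 3 mg = 3,000 µg (Section 6.1). Tablet counts and weight limits from the Section 6.6 table. Stated dose 200 µg/kg (Study Summary, Section 3; approximate in Section 6.1).

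**Formula.** Dose per kg = tablets × 3,000 µg ÷ weight in kg.

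**Where the table reproduces 200 µg/kg.** One tablet: 3,000/15 = 200. Two: 6,000/30 = 200. Three: 9,000/45 = 200. Four: 12,000/60 = 200. Five: 15,000/75 = 200, but the top row begins above 75 kg. The two-, three- and four-tablet rows therefore pass through the stated dose well inside their limits. The one-tablet row meets it only at 15 kg, and the five-tablet row never does.

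**Each row at its limits and midpoint (µg/kg).**

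| Row (kg) | Tablets | Lower limit | Midpoint | Upper limit |
|---|---|---|---|---|
| 15 to 25 | 1 | 3,000/15 = 200 | 3,000/20 = 150 | 3,000/25 = 120 |
| 12.5 to 25 (other reading) | 1 | 3,000/12.5 = 240 | 3,000/18.75 = 160 | 3,000/25 = 120 |
| 25 to 37.5 | 2 | 6,000/25 = 240 | 6,000/31.25 = 192 | 6,000/37.5 = 160 |
| 37.5 to 50 | 3 | 9,000/37.5 = 240 | 9,000/43.75 = 206 | 9,000/50 = 180 |
| 50 to 75 | 4 | 12,000/50 = 240 | 12,000/62.5 = 192 | 12,000/75 = 160 |
| above 75 | 5 | just under 200 | not defined | no upper limit |

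For the top row the documents give no upper weight. At an assumed 100 kg the dose is 15,000/100 = 150; at an assumed 125 kg it is 15,000/125 = 120.

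**Size of the shortfall in the one-tablet row.** At 25 kg: (200 − 120)/200 = 40% below. At the midpoint: (200 − 150)/200 = 25% below if the row starts at 15 kg, or (200 − 160)/200 = 20% below if it starts at 12.5 kg. Between 12.5 and 15 kg, on the second reading, the dose is 240 to 200. Above 15 kg it is below 200 on either reading.

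**Comparison with the middle rows.** Their range is 160 to 240, that is, 200 ± 20%. One tablet falls below 160 once weight exceeds 3,000/160 = 18.75 kg. From there to 25 kg the row gives less than any middle row gives at any weight.

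**Shared end points.**

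| Weight (kg) | Lower row | Upper row | Ratio |
|---|---|---|---|
| 25 | 3 mg, 120 µg/kg | 6 mg, 240 µg/kg | 2.00 |
| 37.5 | 6 mg, 160 µg/kg | 9 mg, 240 µg/kg | 1.50 |
| 50 | 9 mg, 180 µg/kg | 12 mg, 240 µg/kg | 1.33 |

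The weight 75 kg is not ambiguous, because the top row is printed as greater than 75.

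**The case against.** The best reply is that whole tablets over a weight band cannot give exactly 200 µg/kg at every weight, that Section 6.1 calls the figure approximate, and that Section 6.6 describes the bands as standard. This stands for the three middle rows, which vary around 200 and are not in dispute. It does not clearly cover the one-tablet row. Above 15 kg the departure is in one direction only and reaches 40%, and the Study Summary and Section 3 state 200 without qualification. Whether the chart matches an external standard cannot be judged from the protocol.

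A second reply is that the lower limit of that row is uncertain. Its label may be editing residue, and the 12.5 kg reading agrees with the list under the table. This also stands, and it is why both midpoints are shown. It would be wrong to infer that everyone in the row is below 200 µg/kg: on the 12.5 kg reading, those up to 15 kg are not.

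A third reply is that the rows share end points and do not overlap over a range. That is correct. Only people recorded at exactly 25, 37.5 or 50 kg are affected. Their number is unknown, since the protocol gives neither the precision of the scales nor a weight distribution. A reader might take the two-fold gap to apply at all three weights, but it occurs only at 25 kg.

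Finally, a reader might infer that the treatment comparison is biased or the sample size undermined. The documents do not support this. Both arms receive the same scabies regimen from the same table, so the shortfall is common to both. Section 9 gives the fall to about 10% on ivermectin alone as a planning assumption and ties it to no per-kilogram dose, and the 637 per arm does not use the table.

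**Conclusion.** The point holds as an internal contradiction in the dosing instructions. With 3 mg tablets, the ivermectin row ending at 25 kg is below the stated 200 µg/kg at every weight above 15 kg and reaches 120 µg/kg at 25 kg, outside the 160 to 240 range of the middle rows. The row above 75 kg is also always below 200; how far depends on body weights that the protocol does not give. Three weights map to two rows each, with dose ratios of 2.00, 1.50 and 1.33.

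These results rest only on the printed tablet counts, limits and tablet strength. The one unresolved input is the first row's lower limit. It moves the midpoint between 150 and 160 but leaves the shortfall above 15 kg unchanged. No bias between arms and no change to the sample size follows. Nor do the figures show that the table, as opposed to the stated dose, is the entry in error. The case for acting is that the conflict concerns the dosing of children and costs very little to remove.

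**What to change.** The sponsor's responsible clinicians should reconcile the ivermectin column of Section 6.6 with the dose in the Study Summary, Section 3 and Section 6.1. They can either amend the table or state in those three places the per-kilogram range that the bands are meant to deliver. This review does not say which entry is right and proposes no dose.

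In the same edit they should:

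- settle the printed lower limit of the first ivermectin row, so that it agrees with the under-15 kg row, the list below the table and Section 6.9;
- print every band with one end included and the other excluded, so that each weight falls in exactly one row.

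The cost is a correction to one table or three short statements, with the wording of the weight limit made consistent, and a reprinted dosing chart before the first distribution. The design, sample size and analysis do not change.

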#### Duration

The duration of the study is 12 months. For all participants, there will be a 15 day on-study period which will include two visits by the study team

- Day 1 for baseline medical assessment and delivery of azithromycin/tetracycline and ivermectin/permethrin
- Day 8-15 for delivery of second dose of ivermectin/permethrin

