### *Treatment of yaws:*

Single dose of Azithromycin (30mg/kg, max 2G).

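### The azithromycin weight-band table, headed 250 mg tablets, gives 33–67% of the stated 30 mg/kg (maximum 2 g) dose from 12.5 kg upward

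*Combined protocol and SAP*

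**What the plan says.** The Treatment part of Section 3 sets the yaws treatment as "Single dose of Azithromycin (30mg/kg, max 2G"), and the Study Summary gives the same dose. Section 6.1 repeats it: "The recommended dose for the mass treatment of yaws is a single-dose of azithromycin 30mg/kg up to a maximum of 2g". On formulations, Section 6.1 says "Azithromycin is available as 250 mg or 500 mg tablets and as oral suspension".

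Section 6.6 turns the rule into tablets. It states that "the dosing of both Azithromycin and Ivermectin will use the following weight bands", and the azithromycin column is headed "AZITHROMYCIN TABLETS (250mg Tabs"). The counts are 1 tablet below 15 kg, 1 in the next row up to 25 kg, 2 for 25–37.5 kg, 3 for 37.5–50 kg, 4 for 50–75 kg and 4 above 75 kg. The ivermectin column (3 mg tablets) gives 1, 2, 3, 4 and 5 tablets from the second row down. No other part of the protocol gives tablet counts.

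Three smaller points sit beside this:

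- The weight below which permethrin replaces ivermectin is 15 kg in the Summary and Section 3. Section 6.9 agrees ("pregnant and breast feeding women and children <15kg will be offered permethrin rather than ivermectin"), but the list under the Section 6.6 table has "Child <12.5kg".
- The under-15 kg row has no lower limit and overlaps the row after it.
- The Duration part of Section 3 has "Day 1 for baseline medical assessment and delivery of azithromycin/tetracycline and ivermectin/permethrin" and does not say who would receive tetracycline.

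**The concern.** The protocol holds two azithromycin dosing rules that cannot both be followed. Weight-band rounding normally falls on both sides of the target. Here every band from 12.5 kg up falls below it, and the largest printed dose is half the stated cap.

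The table is what a field team would work from. Drugs are taken out in bulk, people are weighed, and tablets are given under observation. Compliance is judged at that moment (Section 6.10), so a team giving the printed count would be recorded as fully compliant.

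Both arms receive ivermectin or permethrin on the same schedule. Azithromycin on Day 1 is the only planned difference between them. If the table were used as printed, the impetigo and resistance results would describe roughly half the yaws dose named in the objective. The contrast assumed in Section 9 (10% against 5% impetigo) might then be smaller. The comparison between arms would not be biased, but it would answer a question about a different dose. Participants in both arms would also receive less than the stated yaws treatment, since the sequential arm is offered azithromycin at month 12.

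**Working it through.** **Inputs.** Dose rule: 30 mg/kg, cap 2,000 mg (Summary, Section 3, Section 6.1). Tablet counts, weight bands and the 250 mg heading: Section 6.6. Alternative strength of 500 mg: Section 6.1. Ivermectin rule of 200 µg/kg: Section 3. Ivermectin 3 mg tablets: Section 6.1.

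**Stated dose.** Dose at weight w = min(30 × w, 2,000) mg. The cap is reached at 2,000 / 30 = 66.7 kg.

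**Table as printed.** Delivered dose = tablets × 250 mg. Share = delivered / stated. Values run from the bottom to the top of each band.

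| Band (kg) | Tablets | Delivered (mg) | Stated (mg) | mg/kg | Share of stated |
|---|---|---|---|---|---|
| 12.5–25 | 1 | 250 | 375–750 | 20–10 | 67–33% |
| 25–37.5 | 2 | 500 | 750–1,125 | 20–13.3 | 67–44% |
| 37.5–50 | 3 | 750 | 1,125–1,500 | 20–15 | 67–50% |
| 50–75 | 4 | 1,000 | 1,500–2,000 | 20–13.3 | 67–50% |
| >75 | 4 | 1,000 | 2,000 | below 13.3 | 50% |

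The overall range from 12.5 kg upward is 33–67%. The unclear lower edge of the first band does not alter this, because the under-15 kg row also gives one tablet. Taken from 15 kg, that band alone runs from 56% to 33%.

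**Same counts at 500 mg.**

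| Band (kg) | Delivered (mg) | mg/kg | Share of stated |
|---|---|---|---|
| 12.5–25 | 500 | 40–20 | 133–67% |
| 15–25 (if the band starts at 15) | 500 | 33.3–20 | 111–67% |
| 25–37.5 | 1,000 | 40–26.7 | 133–89% |
| 37.5–50 | 1,500 | 40–30 | 133–100% |
| 50–75 | 2,000 | 40–26.7 | 133–100% |
| >75 | 2,000 | below 26.7 | 100% |

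At 500 mg the doses lie around the rule, and the maximum is 4 × 500 = 2,000 mg, exactly the stated cap.

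**Ivermectin column as a comparison.** Tablets × 3 mg / weight gives 200–120 µg/kg at 15–25 kg, 240–160 at 25–37.5 kg, 240–180 at 37.5–50 kg and 240–160 at 50–75 kg. That is 60–120% of 200 µg/kg, so this column falls on both sides of its target in every band from 25 to 75 kg. The azithromycin column does the same at 500 mg but not at 250 mg.

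**Smallest children.** One 250 mg tablet exceeds 30 mg/kg below 250 / 30 = 8.3 kg. One 500 mg tablet exceeds it below 500 / 30 = 16.7 kg, and so for every child in the under-15 kg row. At 12.5 kg it gives 40 mg/kg, 133% of the stated dose, and the excess grows as weight falls. Relabelling alone therefore does not repair this row.

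**The case against.** The strongest reply is that the harm is conditional. The 30 mg/kg rule appears three times, and Section 6.6 describes its bands as standard treatment, so the intended dose is not in doubt. If the tablets supplied are 500 mg, the heading is a labelling slip and doses from 25 kg up are 89–133% of the rule. The record form and the product information listed in the Appendices are not available here and might settle the strength. This limits what can be claimed about doses actually given. It does not reconcile the table with the rule, and a slip in a dosing table still has to be corrected.

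Several narrower objections have force:

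- The protocol holds no dose-response information for impetigo or resistance, so a weaker effect at the lower dose is a possibility and not a finding.
- The ivermectin column falls to 60% of its own target at 25 kg, so it supports the mislabelling explanation only modestly. The exact match of four 500 mg tablets to the 2 g cap is better evidence.
- The row overlap carries word-processor formatting residue and may be lost tracked-change marking. It should not weigh much.
- The permethrin limit affects both arms alike. That point and the tetracycline mention are minor tidying and are separate from the strength conflict.

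**Conclusion.** The concern holds. Section 6.6 as printed contradicts the stated azithromycin dose, giving 33–67% of it from 12.5 kg upward and at most 1 g against a 2 g cap. This rests only on the printed counts, the printed strength and the stated rule.

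That the heading is wrong, and not the counts, is a well-supported inference which the protocol does not confirm. Whether anyone would be under-dosed is not known from the documents. The lack of a workable dose for the smallest children stands at either strength. Because the table governs the drug that separates the arms, it must be corrected before use.

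**What to change.** 1. Confirm which tablet strength is supplied. If 500 mg, change the column heading to 500 mg. If 250 mg, double the counts to 2, 4, 6, 8 and 8 from the 15–25 kg band up.
2. Give children below the lowest tablet band 30 mg/kg as oral suspension, which Section 6.1 lists as available.
3. Consider splitting the 15–25 kg band, where 500 mg falls to 20 mg/kg at 25 kg. Giving 500 mg at 15–20 kg yields 33.3–25 mg/kg, and 750 mg at 20–25 kg yields 37.5–30 mg/kg. The 750 mg step is three 250 mg tablets, or one and a half 500 mg tablets. This is optional.
4. Use one weight limit, 12.5 or 15 kg, for permethrin throughout, and state who receives tetracycline or remove the mention.
5. Check that the administration form in Section 6.5 records tablet strength or milligrams given, so that delivered mg/kg can be reported.

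The core correction is one table, one weight limit and a check of the dosing card and record form. Suspension may mean ordering another formulation. If the change counts as a substantial amendment, Section 11.1 requires a favourable opinion from both ethics committees first. Design and sample size do not change.

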## STUDY SUMMARY

**TITLE** Impact of Single-Dose Azithromycin in Impetigo and Skin Microbiology

**DESIGN** A prospective community intervention trial to assess the impact of community mass treatment with azithromycin for yaws and ivermectin for scabies, on non-yaws bacterial skin infections.

**AIMS** Assess the impact of single dose azithromycin, given for yaws, on other prevalent bacterial skin infections.  
Assess the impact of single dose azithromycin on antimicrobial resistance patterns in isolates of *S.pyogenes* and *S.aureus*.

**OUTCOME MEASURES** Primary Outcome  
a) Difference in the change in prevalence of impetigo between baseline and 12-months between the parallel and the sequential treatment arms.

Secondary Outcomes  
b) Change in the proportion of swab samples from which *S. pyogenes* is cultured between baseline and follow-up in the two arms  
c) The proportion of samples from which a drug-resistant isolate of *S.pyogenes* is cultured in the two arms

**POPULATION** Parallel Treatment Arm: Sample size of 637  
Sequential Treatment Arm: Sample size of 637

**ELIGIBILITY** All residents of selected communities are eligible to participate in the study

**TREATMENT** *Treatment of yaws:*  
Single dose of Azithromycin (30mg/kg, max 2G).

*Treatment of scabies:*

Either an oral dose of Ivermectin (200µg/kg) or permethrin cream for those with a contraindication to Ivermectin (WT<15kg, pregnant or breastfeeding women) given in 2 doses 7-14 days apart.

**DURATION** 12 months

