**Contact details for reporting SAEs and SUSARs**  
**[contact] / [name]**  
**Email: [contact]**

## 8. ASSESSMENT AND FOLLOW-UP

### Baseline Data Collection

At baseline (D1) all individuals will undergo a standardized examination to collect data on the presence of skin lesions consistent with yaws, scabies and impetigo. Following examination a finger-prick sample will be obtained from all individuals on to filter paper. In individuals with skin lesions consistent with yaws the same finger prick sample will be used for a rapid diagnostic test for yaws. In individuals with skin lesions consistent with yaws or impetigo two sterile lesion swabs will be obtained.

Following examination individuals will be weighed and directly observed treatment will be dispensed in line with standard treatment guidelines (see above). On D8 study teams will return to each community and offer a second dose of medication for scabies.

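### Section 6.6 lists permethrin for children under 12.5 kg, but its own table and three other places set the limit at 15 kg, two of them as a contraindication to ivermectin

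*Combined protocol and SAP*

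**What the plan says.** Five places in the combined protocol and SAP set the weight below which a child gets permethrin cream instead of ivermectin.

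- **Section 6.6, list of circumstances for permethrin:** "Child <12.5kg". The list also names pregnancy, breastfeeding and age under 6 months.
- **Section 6.6, dosing table, first row:** under 15 kg, permethrin cream.
- **Study Summary, Treatment:** permethrin for "those with a contraindication to Ivermectin (WT<15kg, pregnant or breastfeeding women").
- **Section 3, Treatment of scabies:** "permethrin cream for those with a contraindication to Ivermectin (WT<15kg, pregnant or breastfeeding women").
- **Section 6.9, Trial restrictions:** "As noted above pregnant and breast feeding women and children <15kg will be offered permethrin rather than ivermectin".

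The second row of the Section 6.6 table, for one ivermectin tablet, prints both 12.5 and 15 at its lower end, with 25 kg as its upper end.

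These are working instructions. Section 6.5 states: "For participants receiving ivermectin and azithromycin, the dose will be determined according to body weight". Section 6.6 adds that "the dosing of both Azithromycin and Ivermectin will use the following weight bands". Section 8 describes what happens at baseline: "Following examination individuals will be weighed and directly observed treatment will be dispensed in line with standard treatment guidelines (see above"). The choice of scabies drug arises again at the second visit, listed in Section 3 under Duration as "Day 8-15 for delivery of second dose of ivermectin/permethrin".

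**The concern.** The weight limit decides which drug a small child receives, and the protocol prints two values for it. They appear a few lines apart in the section that staff would consult for dosing. No statement says which one governs.

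A team that follows the table, the Summary, Section 3 or Section 6.9 gives permethrin to a 13 kg child. A team that treats the list as the definition of who gets permethrin finds no weight reason to withhold ivermectin from the same child, although the Summary and Section 3 call that child contraindicated. Practice could then differ between teams, or between the two visits.

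The protocol has little else to catch such a slip. Section 7.3.1 limits collection to SAEs and SUSARs, Section 10.1 provides for passive monitoring only, and Section 12 appoints no DSMB. What is at stake is consistent protection of participants, not the trial's inference.

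**Working it through.** **1. The statements side by side, for a child aged 6 months or more weighing 12.5 to under 15 kg**

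| Place | Limit | What it says for this child |
|---|---|---|
| Study Summary | <15 kg, contraindication | Permethrin |
| Section 3, Treatment of scabies | <15 kg, contraindication | Permethrin |
| Section 6.6 table, first row | <15 kg | Permethrin |
| Section 6.9 | <15 kg | Permethrin |
| Section 6.6 list | <12.5 kg | Not listed |

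Four statements assign permethrin and one list leaves the child out. Children under 6 months are on the list at any weight, so the mismatch does not reach them.

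**2. Width of the band**

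15 − 12.5 = 2.5 kg, at two visits (Day 1 and Day 8-15). The documents do not say how many children fall in it.

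**3. Dose, if such a child were given ivermectin**

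Inputs: 3 mg tablets (Section 6.1) and a stated dose of 200 µg/kg (Study Summary; Section 3). One tablet per child is an assumption; it is the lowest dose in the table. Dose per kg = 3,000 µg ÷ weight.

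- 12.5 kg: 3,000 ÷ 12.5 = 240 µg/kg, and 240 ÷ 200 = 1.20, so 20% above the stated dose.
- 14 kg: 3,000 ÷ 14 = 214 µg/kg.
- 15 kg: 3,000 ÷ 15 = 200 µg/kg, exactly the stated dose.
- 25 kg: 3,000 ÷ 25 = 120 µg/kg.

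The one-tablet row thus spans 120 to 200 µg/kg if it starts at 15 kg, and 120 to 240 µg/kg if it starts at 12.5 kg.

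**4. The same calculation at the bottom of the next three bands**

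6,000 ÷ 25 = 9,000 ÷ 37.5 = 12,000 ÷ 50 = 240 µg/kg. The highest dose in the disputed band is one that the table already gives elsewhere.

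**5. Which limit the document favours**

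- *For 15 kg:* four of five statements, including the table in Section 6.6 itself; the word contraindication in two of them; and one tablet equal to 200 µg/kg at exactly that weight.
- *For 12.5 kg:* the single list item, and the table's spacing. Two, three and four tablets start at 25, 37.5 and 50 kg, which are 2, 3 and 4 times 12.5, so one tablet at 12.5 kg would continue the series.

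The four statements are not fully independent: Section 3 repeats the Summary, and Section 6.9 refers back to earlier text. Even so, the balance is towards 15 kg.

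**6. Effect on the trial comparison**

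Section 3 gives both arms the same scabies schedule: two doses of ivermectin or permethrin, 7 to 14 days apart. Azithromycin is one tablet in both the first and second table rows, so moving the boundary between them changes no azithromycin dose.

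**The case against.** The strongest reply is that the text is an unfinished edit and that its meaning is plain. The doubled lower bound in the second table row and two stray formatting markers, one of them directly after the list, look like revision mark-up that was never accepted. Text taken from a PDF does not show struck-out characters, so one cannot exclude that part of this passage was being replaced. A team would also have to apply the list while overlooking a table row a few lines above it, and the MDA Record Form (Appendix 4), which may be what staff actually use, is not shown.

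Much of this stands. The second table row cannot serve as evidence for either limit, and how the drug was dispensed in the field is unknown. It does not remove the mismatch. The list item and the first table row each print one clean value, and the values differ. Either reading of the second row conflicts with one of them: a start at 15 kg conflicts with the list, and a start at 12.5 kg overlaps the row above it.

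A reader might go further and infer that these children have directly opposite instructions. The documents do not support that. The list says when permethrin is used; it does not say that these are the only cases, and it directs nobody to ivermectin. Nor is it a full list of exclusions: Section 6.8 bars ivermectin for people on warfarin, who are not on it. The only text that could assign ivermectin to this band is the garbled row.

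**Conclusion.** The mismatch is real and should be corrected. Section 6.6 disagrees with itself and with three other places about the weight below which permethrin replaces ivermectin, and children of 12.5 to under 15 kg aged 6 months or more are missing from the list that is meant to identify them. Confidence is high for what is printed, and not for what teams did.

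The size is small. On the one-tablet assumption, the excess over 200 µg/kg is at most 20%, at a level the table accepts for heavier participants. The problem is the stated contraindication, not the dose per kg.

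Two further inferences are tempting and unsupported. One is that the two limits are equally plausible; the text favours 15 kg, though only the sponsor can confirm it. The other is that the inconsistency could bias the result; the scabies schedule is the same in both arms, and nothing ties the choice of limit to arm. No effect on the sample size or primary analysis follows.

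**What to change.** **Default, 15 kg (two line edits, both in Section 6.6).** Change the list item to under 15 kg, and print the second table row as 15 to 25 kg. The section then agrees with the other four statements and with one 3 mg tablet giving 200 µg/kg at the boundary.

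**Only if the sponsor confirms that 12.5 kg was intended (five line edits).** Change the Study Summary, Section 3, the first table row and Section 6.9 to 12.5 kg, print the second table row as 12.5 to 25 kg, and stop describing under 15 kg as a contraindication.

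In either case, check that the MDA Record Form carries the same limit. If the sponsor judges the change a substantial amendment, Section 11.1 requires a favourable opinion from both ethics committees before it is used. There is no cost to sample size, visit schedule or analysis.
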